The Client Service Receipt Inventory (CSRI) is a research instrument developed to collect information on service utilisation, income, accommodation and other dimensions relevant to the estimation of costs [36]. Its primary purpose is to allow service use

patterns to be measured and described and service and support costs to be derived by combining appropriate unit costs with service use and support data. The CSRI takes around 20 minutes to complete.

Short Form 36 (SF-36)

The SF-36 is a patient-reported survey of patient health and consists of eight scales yielding two summary measures: physical and mental health. The SF-36 offers a choice of recall format at a standard (4 week) or acute (1 week) time frame. We will use the standard (4 week) time frame. Likert scales and yes/no options are used to assess function and well-being. Data generated from this questionnaire will be revised into a six-dimensional health state classification (the SF-6D) and societal weights will be attached [46]. The SF-36 takes around 10 minutes to complete.

Exit interview

An exit interview will be conducted (including cases who complete the 12 month treatment) to assess blinding (including that of the rater), experience of participation, and reasons for early discontinuation if applicable (including lack of efficacy, adverse effects, switch to another antipsychotic or personal reasons). If subject is lost to follow up then loss to follow up will recorded in lieu of an exit interview.

HoNOS

This is a national NHS standard measure of symptoms and function in psychiatric patients. It is measured yearly by mental health care teams as part of routine care and will be assessed annually during the study -extension. It is an instrument with 12 items measuring behaviour, impairment, symptoms and social functioning. We will ensure that all patients have their HoNOS assessments recorded prior to enrolling them.

9 Assessment of Safety

The Investigator or appropriate designee will review results of safety assessments on a regular basis and the Sponsor must be kept fully informed of any clinically significant findings either at Screening or subsequently during study conduct.

9.1 Safety Parameters.

Adverse Events

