Costs will be captured from two perspectives: NHS & personal social services (PSS) and a wider societal perspective that will include criminal justice services, caregiver out-ofpocket expenses and lost productivity. The client service receipt inventory (CSRI) adapted for use in this study will be used to collect service use and support data for each participant in the study that will be used to generate cost from these two perspectives [36]. The CSRI facilitates the standardised recording of service use that is commensurate with accurate cost estimation. Through a patient interview, data on service use and caregiver support will be collected for the 3-month period prior to assessment at baseline (for the period prior to entering the study), and at 6 and 1-year follow-up interviews. During the treatment period, we use data collected on the treatment dosages and titration schedules. Also at baseline, 3-month 6-month and 1year, the SF-36 (36-item short form health survey) will be transformed into a single preference-based measure of health using the algorithm developed by Brazier and colleagues [46]. Using the area under the curve method with linear interpolation between assessment points (and baseline adjustment for comparisons), the qualityadjusted life-year (QALY) gain for each patient will be generated.

From each perspective, in turn, the cost-effectiveness evaluation will compare the comprehensively measured service and support costs between the placebo plus continuing antipsychotic treatment arm and the valproate plus continuing antipsychotic treatment arm with, first, the difference between the treatments in the primary outcome measure (psychotic symptom severity as measured by the PANSS positive subscale), and then with the difference between the treatments in QALYs gained. In each case, an incremental cost-effectiveness ratio (ICER) will be computed as the mean cost difference between placebo plus continuing antipsychotic treatment arm and the valproate plus continuing antipsychotic treatment arm divided by the mean difference in change in primary and secondary outcome respectively. The cost-effectiveness measures will be incremental cost per point improvement in PANSS positive subscale (by 3, 6 month and 1-year) and incremental cost per QALY gain by 12 months. We will use the current standard NICE cost-effectiveness threshold range of £20K and £30K per OALY to determine if the intervention meets cost-effectiveness criteria.

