For the base-case models under both perspectives, we will compare costs and outcomes between the treatment arms at baseline, 3-month, 6- month and 12-months follow-up. In these models we will control for baseline costs (only in the cost analysis); centre; baseline PANSS psychotic symptom severity rating; treatment; time (categorical); and time*treatment interactions.

Bootstrapping with mixed effects models will be used to generate confidence intervals that can be used to capture parameter uncertainty around the estimates in the cost-

effectiveness analysis. The 1000 treatment effect replications from this bootstrapping process will be plotted on cost-effectiveness planes and used to construct cost-effectiveness acceptability curves (CEAC). We will use cost effectiveness acceptability curves (CEACs) to explore the nature of the trade-off faced by the decision-maker in situations where one treatment option is both more effective and costly than the other. In this case, the decision maker would need to consider if it is worth incurring the higher costs to improve outcomes. Using this approach, we will be able to show the likelihood of valproate plus continuing antipsychotic treatment arm being seen as cost-effective relative to the placebo plus continuing antipsychotic treatment arm given different (implicit monetary) values placed on incremental outcome improvements. Bootstrapping and regression analysis will be used to generate CEACs. We will also explore the sensitivity of the results to changes in key parameters and the analyses will be repeated. This will include the same control variables as those in the base-case model.

11 Trial Steering Committee

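### The base-case control list for the cost-effectiveness models omits baseline SF-6D utility, although the same section promises baseline adjustment of QALY comparisons

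*Protocol*

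**What the plan says.** All of this is in Protocol Section 10.3, under the cost-effectiveness evaluation, unless another section is named.

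- **Utility data.** "Also at baseline, 3-month 6-month and 1year, the SF-36 (36-item short form health survey) will be transformed into a single preference-based measure" of health. Section 8.1.2 identifies the measure as a "six-dimensional health state classification (the SF-6D"). The visit schedule in Section 4.3 and the Visit 2 list in Section 7.1 both include the SF-36 at baseline, so baseline utility will be available.
- **QALY construction.** "Using the area under the curve method with linear interpolation between assessment points (and baseline adjustment for comparisons"), a QALY gain is generated for each patient. The QALY result to be reported is the "incremental cost per QALY gain by 12 months".
- **Scope of the base-case models.** "For the base-case models under both perspectives, we will compare costs and outcomes between the treatment arms", so one specification serves costs, PANSS and QALYs.
- **Controls.** "In these models we will control for baseline costs (only in the cost analysis); centre; baseline PANSS psychotic symptom severity rating; treatment; time (categorical") and the time-by-treatment interaction.
- **Sensitivity analyses.** "This will include the same control variables as those in the base-case model".

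**The concern.** The list is detailed enough to limit one covariate, baseline costs, to one analysis. Under it the cost model is adjusted for baseline cost and the PANSS model for baseline PANSS. Only the QALY model lacks the baseline value of its own outcome. The promise of baseline adjustment a few sentences earlier does not say how the adjustment is made, and the list that should implement it leaves it out.

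Baseline utility is a component of every patient's area under the curve and is likely to predict the later utilities. Leaving it out gives a wider confidence region and a flatter acceptability curve than the data allow. It also lets a chance difference in baseline utility move the realised QALY difference. Cost-effectiveness is one of the trial's stated objectives (Section 4.1), and the result is to be judged against £20,000 to £30,000 per QALY.

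**Working it through.** There is no stated figure to reproduce, since the point concerns a covariate list. The size can be bounded as follows.

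**Inputs from the protocol:** utilities at 0, 3, 6 and 12 months (Section 10.3); 290 analysed, so 145 per arm (Section 10.1 and the flow diagram in Section 4.2).

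**Assumptions:** equal variance at each visit and a common correlation r between visits, taken as 0.4 to 0.7. The protocol gives 0.4 in its PANSS power calculation and nothing for utility. The SF-6D standard deviation is assumed to be 0.12, with 0.10 to 0.15 as a range.

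**Weights.** The intervals are 0.25, 0.25 and 0.5 years, so the trapezoidal weights are 0.125, 0.25, 0.375 and 0.25. They sum to 1, and their squares sum to 0.28125.

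**Moments, in units of the utility variance.**
- Variance of the AUC: v = r + (1 − r) × 0.28125 = 0.569 (r = 0.4) or 0.784 (r = 0.7).
- Slope of the AUC on baseline: c = 0.125 + 0.875r = 0.475 or 0.7375.
- Residual variance after covariate adjustment: v − c² = 0.343 or 0.240.

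**Standard error of the QALY difference, covariate adjustment against each alternative.** These ratios do not depend on the SD.

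| Alternative | Variance | Reduction, r = 0.4 | Reduction, r = 0.7 |
|---|---|---|---|
| No baseline adjustment | v | 1 − √(0.343/0.569) = 22% | 1 − √(0.240/0.784) = 45% |
| AUC minus baseline | v + 1 − 2c = 0.619 or 0.309 | 1 − √(0.343/0.619) = 26% | 1 − √(0.240/0.309) = 12% |
| Covariate adjustment already intended | v − c² | 0% | 0% |

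**Chance imbalance.** The standard error of a baseline difference is 0.12 × √(2/145) = 0.0141, so the 95% limit is 1.96 × 0.0141 = 0.028. With no adjustment, an imbalance of that size shifts the QALY difference by 0.475 × 0.0276 = 0.013 to 0.7375 × 0.0276 = 0.020. At £20,000 per QALY that is about £260 to £410 per patient, and at £30,000 about £390 to £610. These scale in proportion to the SD. With AUC minus baseline the slope is c − 1 = −0.525 or −0.2625, so the same imbalance shifts the difference by about 0.014 or 0.007 in the opposite direction.

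**Does baseline PANSS stand in?** Suppose it correlates −0.2 to −0.4 with baseline utility (assumed) and acts on QALYs only through it. At r = 0.4 it then removes about 2% to 6% of QALY variance, against c²/v = 0.226/0.569 = 40% for baseline utility itself.

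**The case against.** The best defence is that the adjustment is already there. The sentence defining the QALY commits to it, the natural baseline for a QALY comparison is baseline utility, and the list is not said to be exhaustive or to override that sentence. This has force: the principle is stated, so what is at issue is an incomplete specification and not a decision against adjustment. But the list is explicit, covers cost and outcome models alike, and is the specification that the sensitivity analyses repeat.

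Two other readings are possible. The adjustment might mean subtracting baseline to form the gain. As the working shows, that over-corrects and leaves imbalance acting with the opposite sign. Or baseline might be one of the modelled time points, since arms are to be compared at baseline as well as at follow-up. That cannot apply to a 12-month area under the curve, which is one value per patient and has no time dimension. If utilities were instead modelled visit by visit with baseline as a response, adding it as a covariate would use it twice, so the fix should state the model form.

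The covariates of a QALY regression may also be left to the analysis plan. Here, though, the protocol has not left them open; it has listed them.

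**Conclusion.** The point holds as a minor one. The list does not carry out the baseline adjustment promised in the same section, and the constructions that the text allows give different QALY differences and different precision.

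A reader might infer that the planned QALY contrast is biased, that imbalance passes into it in full, or that 45% is the precision to be lost. The documents support none of these. Randomisation keeps the unadjusted contrast unbiased on average. Under the stated assumptions, 0.475 to 0.74 of an imbalance passes through. The 22% to 45% range applies only if no baseline adjustment is made at all, contrary to the QALY definition; it is 26% to 12% if baseline is subtracted, and nil if covariate adjustment is what the sponsor means. The shifts in pounds describe an imbalance at the 95% limit. They are not additional to the loss of precision, because a bootstrap interval already reflects chance imbalance.

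All sizes rest on assumed utility correlations and, for the shifts, an assumed SD. They are stated before any contribution from baseline PANSS.

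**What to change.** In the base-case control list, add *baseline SF-6D utility (only in the QALY analysis)*, parallel to the existing entry for baseline costs. State that the 12-month QALY is analysed as one area-under-the-curve value per patient with this covariate, not as the area minus baseline, so that the time and time-by-treatment terms do not apply to that model. Once the covariate is in, subtracting baseline as well would leave the treatment coefficient unchanged, so the covariate is the part that matters. The sensitivity analyses then inherit the correction.

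The cost is one phrase and one sentence. The SF-36 is already collected at Visit 2, and no new data or change to the sample size is needed. If the sponsor already intends covariate adjustment, the edit simply records it before unblinding.

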Appendix 1 Dose titration chart for 500mg sodium valproate tablets

Body Weight Range (kg)	Days 1 -3	Days 4 – 6	Days 7 – 9	Days 10 – 12	Days 13 - 15	Day 16 onwards	Maximum number of tablets that can be taken so it does not exceed 30mg/kg/day or 2500mg/day
35-49	1	1	2	2	2	2	2
50-69	1	1	2	2	3	3	3
70-84	1	1	2	2	3	3	4
85-99	1	1	2	2	3	3	5
100-134	1	2	3	3	4	4	5
>134	1	2	3	4	4	5	5

The titration is a guideline so that all weight categories exceed 15mg/kg/day. Doses will be guided by individual patient's ability to tolerate the medication. Changes to doses (increase or decrease) in individual patients can be made after the titration phase as long as it does not exceed the 30mg/kg/day or 2500mg/day threshold

After V3 (visit 3 - end of titration phase) any changes in dose will be followed by a telephonic assessment (face-to-face especially for in-patients) after 3 to 7 days on the new dose of medication to assess tolerability and suitability to continue that dose.

Appendix 2 - SAE Reporting schematic

The **AE** event is **SERIOUS** if any of the following criteria applies:

- 1. The participant died
- 2. The participant was at risk of death because of the AE
- 3. The AE lead to admission or extension of admission to hospital
- 4. The AE resulted in persistent or significant disability/incapacity
- 5. The AE is an important medical event that may jeopardise the participant (or an unborn child) and may require medical or surgical intervention to prevent one of the outcomes listed above

The event should be classed as a **SUSPECTED ADVERSE REACTION** if a possible relationship with the IMP cannot be ruled out.

If the nature of the adverse reaction is consistent with the SmPC or other relevant product information of the IMP or antipsychotic medication, then the event should be classed as an UNEXPECTED REACTION.

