5.3 IMP Risks

The Summary of Product Characteristics (SmPC) for 500 mg Gastro-resistant tablets (Sodium Valproate Wockhardt 500mg Gastro-Resistant Tablets, SmPC revised on 19/12/2018) will be the reference document.

Teratogenic risk

There is a potential risk to unborn children associated with valproate treatment. This risk will be minimised in the following ways:

1) Women of childbearing potential will be supported on the Pregnancy Prevention Programme as outlined by the Medicines and Healthcare products Regulatory Agency MHRA [42]. This ensures that they are aware of the potential risks and ensure that they use a highly effective method of contraception that meets the MHRA guidelines. A serum pregnancy test is also conducted as part of the programme. An annual risk acknowledgment form is also needed as part of the programme. The patient's clinical care team and the research team will monitor compliance to the programme. Neither condoms nor oral contraceptives alone are sufficient. Long-term contraceptives (such as copper intrauterine device [IUD] or levonorgestrel intrauterine system and contraceptive implant [progestogen-only implant], or sterilisation) are recommended and patients will be supported to access these if they wish to consider them and are not

already receiving them. If subjects do not meet the pregnancy prevention programme within the screening period after consenting to the study then they will be considered as screen failed and will be rescreened once the requirements are met.

2) An optional urine pregnancy test based on individual patient's risk assessment and circumstances during the trial (e.g. if there is a gap or change in contraception) will be offered.

Abnormal blood cell counts and liver function

There is a potential, rare risk for bleeding, thrombocytopenia, leucopenia and hepatic failure due to valproate. To reduce this potential risk, we will screen-out and exclude people who may be vulnerable to this by reviewing their clinical history and conducting full blood count and liver function tests (LFTs), if indicated, prior to enrolling patients in the study. We will also monitor both tests at 3, and 12 months after initiation of trial drug or if patient exits the trial early.

Other side effects

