9.2 Procedures for Recording and Reporting Adverse Events

The Medicines for Human Use (Clinical Trials) Regulations 2004 and Amended Regulations 2006 gives the following definitions:

Averse Event (AE): Any untoward medical occurrence in a subject to whom a medicinal product has been administered including occurrences which are not necessarily caused by or related to that product.

Adverse Reaction (AR): Any untoward and unintended response in a subject to an investigational medicinal product which is related to any dose administered to that subject.

Unexpected Adverse Reaction (UAR): An adverse reaction the nature and severity of which is not consistent with the information about the medicinal product in question set out in the summary of product characteristics (SmPC) for that product.

Serious adverse Event (SAE), Serious Adverse Reaction (SAR) or Unexpected Serious Adverse Reaction (USAR): Any adverse event, adverse reaction or unexpected adverse reaction, respectively, that

- Results in death;
- Is life-threatening;
- Required hospitalisation or prolongation of existing hospitalisation;
- Results in persistent or significant disability or incapacity;
- Consists of a congenital anomaly or birth defect.

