Appendix 2 gives a schematic of AE categorization and reporting procedure.

Important Medical Events (IME) & Pregnancy

Events that may not be immediately life-threatening or result in death or hospitalisation but may jeopardise the patient or may require intervention to prevent one of the other outcomes listed in the definition above should also be considered serious.

During the study, if the subject has a hospitalization procedure (e.g. elective surgery) that was scheduled before the study entry, i.e. before consent for an event/condition that occurred before the study, the hospitalization is considered a therapeutic intervention and not the result of SAE. However, if the event/condition worsens during the study, it should be reported as an AE (of SAE if the outcome so warrants).

Although not a serious adverse event, any unplanned pregnancy will also be reported via the SAE reporting system. Each pregnancy will be followed up until the outcome is

known. The CI or PI will liaise with the relevant obstetrician throughout the pregnancy. In the event of a congenital anomaly or birth defect detected in the foetus or live born child it will be reported as an SAE. The database record of all pregnancies will be held by the KHP-CTO, this will include follow up to term and where appropriate, long-term follow up of the baby.

Urgent safety measures

Regulations allow the sponsor and investigator to take appropriate urgent safety measures to protect clinical trial subjects from any immediate hazard to their health and safety. The CI must inform the KHP-CTO as soon as possible after the implementation of the urgent safety measures. The CI or sponsor will phone the MHRA's clinical trial unit on [name] to discuss the issue with a safety scientist, ideally within 24 hours. The MHRA will inform the CI or Sponsor how the submit the substantial amendment to them within 3 days when spoken to them but instructions will be sent by email. The sponsor will then notify the MHRA and the REC in writing, of the measures taken and the reason for the measures within 3 days by submitting a substantial amendment. The decision to undertake appropriate safety measures may be taken by:

- The CI and/or PI
- The KHP-CTO on behalf of the sponsor and in consultation with the CI or DMC

Ongoing safety

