The KHP-CTO will ensure that the CI promptly notifies all other investigators, REC and MHRA of any findings that may affect the health of subjects. A concise safety analysis and risk-benefit evaluation describing all new findings related to the safety of the IMP treatment with respect to their impact for the subjects will be considered by the PIs, CI and DMEC (if applicable).

Reporting Responsibilities

SLAM & KCL have delegated the delivery of the Sponsor's responsibility for Pharmacovigilance (as defined in Regulation 5 of the Medicines for Human Use (Clinical Trials) Regulations 2004 to the King's Health Partners Clinical Trials Office (KHP-CTO).

All SAEs, SARs and SUSARs will be reported immediately (and certainly no later than 24hrs) by the Investigator to the KHP-CTO and CI for review in accordance with the current Pharmacovigilance Policy. This includes completion of an SAE form and sent immediately to the KHP-CTO

by fax on [name]

or by email: [contact]

The original SAE Report Form will be filed in the Trial Master File, with copies filed in the patient's hospital notes, the case record form, the Investigator Site File (if applicable) and the Sponsor file.

The KHP-CTO will report SUSARs to the MHRA. The Chief Investigator will report to the relevant ethics committee. Reporting timelines are as follows:

- SUSARs which are fatal or life-threatening must be reported not later than 7 days after the sponsor is first aware of the reaction. Any additional relevant information must be reported within a further 8 days.
- SUSARs that are not fatal or life-threatening must be reported within 15 days of the sponsor first becoming aware of the reaction.

The Chief Investigator and KHP-CTO (on behalf of the *co*-sponsors), will submit annual progress report relating to this trial to the REC and will contain a summary of AEs that occur in that period.

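### Appendix 2 applies a narrower test of seriousness than Section 9.2: it leaves out congenital anomaly and requires both important-medical-event conditions where either should suffice

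*Protocol*

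**What the plan says.** The protocol states the test of seriousness in two places.

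**Section 9.2, Procedures for Recording and Reporting Adverse Events.** The definitions, taken from the UK clinical trials regulations, list five outcomes that make an event serious. The last is "Consists of a congenital anomaly or birth defect". Under the sub-heading on important medical events and pregnancy, the section adds events that do not immediately reach those outcomes: an event that "may jeopardise the patient or may require intervention to prevent one of the other outcomes listed in the definition above should also be considered serious". The same sub-section says that a "congenital anomaly or birth defect detected in the foetus or live born child it will be reported as an SAE", and that "Although not a serious adverse event, any unplanned pregnancy will also be reported via the SAE reporting system".

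**Appendix 2, SAE Reporting schematic.** Section 9.2 introduces it with the sentence "Appendix 2 gives a schematic of AE categorization and reporting procedure". The appendix gives five numbered criteria, any one of which makes an event serious. Items 1 to 4 are outcomes. Item 5 is the important-medical-event rule: "The AE is an important medical event that may jeopardise the participant (or an unborn child) and may require medical or surgical intervention", the intervention being one that prevents an outcome in the items above it.

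Seriousness sets the reporting clock. Under Reporting Responsibilities in Section 9.2, "All SAEs, SARs and SUSARs will be reported immediately (and certainly no later than 24hrs) by the Investigator".

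**The concern.** The appendix is the page a site would naturally have at hand when classifying an event, and nothing in it says that its list is partial or that Section 9.2 prevails. Where the two differ, the person classifying gets a different answer depending on the page used.

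Both differences push towards under-classification, and an event wrongly called non-serious does not trigger the 24-hour report. The missing outcome is also one the protocol itself raises for this drug. Section 5.3, IMP Risks, says: "There is a potential risk to unborn children associated with valproate treatment".

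**Working it through.** No arithmetic beyond counting applies, so the check sets the two texts side by side.

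| Criterion | Section 9.2 | Appendix 2 |
|---|---|---|
| Death | yes | yes (item 1) |
| Threat to life | yes | yes (item 2) |
| Admission or longer stay in hospital | yes | yes (item 3) |
| Lasting or significant disability | yes | yes (item 4) |
| Congenital anomaly or birth defect | yes | **absent** |
| Important medical event: link between the two conditions | *or* | ***and*** (item 5) |
| Outcomes that the important-medical-event rule refers back to | 5 | 4 (items 1 to 4) |

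**Omitted outcome.** Section 9.2 lists 5 outcomes and Appendix 2 carries 4, so 5 − 4 = 1 is missing. Item 5 mentions the unborn child but does not fill the gap. It concerns intervention to prevent something in items 1 to 4, and an anomaly is not among them. An anomaly already present is not caught, and neither is intervention aimed only at preventing one. The matching rule in Section 9.2 refers back to all five outcomes.

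**Link between the conditions.** Write J for an event that may jeopardise the patient and I for one that may need intervention to prevent a listed outcome.

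| J | I | Section 9.2 (J or I) | Appendix 2 item 5 (J and I) |
|---|---|---|---|
| no | no | not serious | not serious |
| yes | no | serious | **not serious** |
| no | yes | serious | **not serious** |
| yes | yes | serious | serious, if the outcome to be prevented is in items 1 to 4 |

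The two texts disagree whenever exactly one condition is met. In the last row they also disagree if the only outcome to be prevented is a birth defect.

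**Direction.** Any event that meets item 5 may need intervention to prevent one of items 1 to 4. It therefore meets condition I in Section 9.2 and is serious there as well. This remains true when the jeopardy is to the unborn child rather than the participant. Items 1 to 4 match the first four outcomes of Section 9.2. Hence everything serious under Appendix 2 is serious under Section 9.2, but not the reverse: the appendix test is strictly narrower.

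**The case against.** The case against this being more than copy-editing has several parts.

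- **The appendix is a summary.** It says an event is serious if a criterion applies, not only if one does, and Section 9.2 holds the full definition. That reading is strained for a list whose purpose is to classify events: a user who finds no matching item will conclude that the event is not serious. It is fair that Section 9.2 is complete, so no definition is missing from the protocol.
- **Anomalies are caught elsewhere.** Section 9.2 makes an anomaly in a foetus or live-born child an SAE in terms, sends unplanned pregnancies through the SAE system and follows them to outcome. Section 9.1 repeats the pregnancy reporting and requires effective contraception and a valid risk form before dispensing. This stands, and it removes most of the practical effect of the omission. It also shows that the sponsor means anomalies to be SAEs, so the appendix departs from that intention.
- **The link word rarely matters.** An important event that may jeopardise a participant will nearly always be one that may need intervention. This stands as to frequency. It does not reconcile the two wordings.
- **Listed events are exempt anyway.** Section 9.2.1, read literally, exempts from reporting any event in the product information for valproate or the antipsychotic. On that reading the link word can matter only for unlisted events. Those are, however, the events where prompt reporting counts most.
- **Other material may govern.** Sites also work from an SAE form and a pharmacovigilance policy that are not part of the protocol, and these may be correct. Section 9.2 also says the appendix shows the reporting procedure, yet its text contains no reporting steps, so part of the schematic may not be reproduced. An anomaly branch outside the list cannot be wholly excluded. The list itself runs from 1 to 5 without a gap, and the wording of item 5 is unaffected.

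**Conclusion.** The point holds as a minor defect. Appendix 2 omits one of the five seriousness outcomes in Section 9.2, and its important-medical-event item requires two conditions where Section 9.2 accepts either.

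The number of events affected cannot be derived from the protocol and is probably very small. Harm arises only if a site classifies from the appendix without going back to Section 9.2. Even then it is largely confined to events that meet one of the two conditions and are not in the product information, because the separate pregnancy and anomaly instruction covers most of the rest.

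Confidence in the wording is high. There is no bearing on sample size, power, the primary analysis or the efficacy data. The appendix's statement on which reactions are expected is a different matter and is not part of this point.

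**What to change.** Bring Appendix 2 into line with Section 9.2, which needs no correction on these two points:

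1. Insert congenital anomaly or birth defect as a separate item above the present item 5, so that the back-reference in that item also covers it.
2. In the important-medical-event item, replace the *and* joining the two conditions with *or*, keeping the mention of the unborn child.

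With *or* in place, the mention of the unborn child makes the appendix slightly wider than Section 9.2, which speaks of the patient only. That errs on the safe side. If an exact match is wanted, the same words can be added to Section 9.2.

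The cost is two lines in an appendix, with no new data and no extra staff.
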